8.10.2 Quantitative Assessment of Images

The Screening MUBADA SUV_r will be summarized using descriptive statistics [n, mean, SD, median, minimum and maximum values, and quartiles (25th and 75th percentile)] by visual read results (τ AD+, τ AD++ subject eligibility and overall).

8.10.3 Other Efficacy Variables

8.10.3.1 Increased Neocortical Activity

Increased neocortical flortaucipir activity by hemisphere and region will be presented in a listing.

8.11 Analysis of Safety

8.11.1 Extent of Exposure and Compliance to Study Treatment

The total dose administered (MBq) of Flortaucipir F 18 will be summarized using descriptive statistics. All exposure data captured on the CRF will be presented in listings for the safety population.

Because this is a study with only one bolus of study medication per imaging visit, compliance will not be summarized.

8.11.1.1 Unit Conversion and Volume Calculation

All exposure tables will display volume in MBq. Radioactive dose collected in millicuries (mCi) will be converted to MBq as follows:

$$MBq = 37 \times mCi$$

8.11.2 Adverse Events

TEAEs will be summarized by descending frequency, then alphabetically by SOC and preferred term. A subject will only be counted once per SOC and once per preferred term. Subject counts and percentages will be presented for the following summaries:

1. All TEAEs by system organ class (SOC) and preferred term;
2. All TEAEs by preferred term (in order of descending frequency);
3. All TEAEs by relationship to study drug, SOC, and preferred term;
4. All TEAEs by relationship to protocol procedure, SOC and preferred term;
5. All TEAEs by severity, SOC and preferred term
6. All Serious TEAEs by system organ class (SOC) and preferred term;
7. All TEAE leading to study termination by system organ class (SOC) and preferred term

For the summary of TEAEs by severity, if a subject has multiple events occurring in the same SOC or same preferred term, the event with the highest severity will be counted.

TEAEs by relationship to study drug and protocol procedure will be summarized as Related vs. Not Related. If a subject has multiple events occurring in the same SOC or same preferred term, the related event will be summarized.

All AE will be presented in the listings.

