### **7.7.2. Adverse Event Definitions**

#### Adverse Events

An adverse event is any undesirable experience occurring to a subject during a clinical trial, whether or not considered related to the study drug.

For reporting purposes, Avid will distinguish among pre-existing conditions, trial-emergent adverse events and treatment-emergent adverse events.

Pre-existing conditions (i.e., undesirable experiences, signs or symptoms that begin prior to the Screening Visit) will be recorded on the medical history eCRF pages. During the study, site personnel will record any change in the condition(s) and occurrence and nature of any AEs. Signs and symptoms that are believed to be due to the pre-existing condition(s) (started prior to dose of study medication) do not have to be recorded in the AEs section of the eCRF, unless there is an increase in frequency and/or severity.

Trial-emergent adverse events are undesirable experiences, signs or symptoms that begin, or worsen in intensity or frequency, after the informed consent, and prior to administration of the study drug at the imaging visit.

Treatment-emergent adverse events are any untoward medical occurrence associated with the use of a drug in humans, whether or not considered drug related. For the purposes of this study, untoward medical occurrences will be considered associated with the use of flortaucipir F 18, and thus be reported as treatment-emergent adverse events, if they occur within 48 hours after flortaucipir F 18 administration.

The end of study, for the purpose of adverse event reporting, is defined as 48 hours after the last administration of flortaucipir F 18.

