### **7.7.4. Reporting of Serious Adverse Events**

Study site personnel must alert Lilly or its designee of any SAE within 24 hours of their awareness of the event via a sponsor-approved method. Alerts issued via telephone are to be immediately followed with official notification on study-specific SAE forms.

Serious adverse events occurring after a subject receive a dose of investigational product will be collected until 48 hours after the dosing of the investigational product, regardless of the investigator's opinion of causation. Therefore, SAEs that occur later than 48 hours after the dosing of the investigational product are not required to be reported unless the investigator feels the events were related to either investigational product or a protocol procedure.

If a patient experiences an SAE after signing informed consent, but prior to receiving investigational product, the event will NOT be reported unless the investigator feels the event may have been caused by a protocol procedure. Previously planned (prior to signing the ICF) surgeries should not be reported as SAEs unless the underlying medical condition has worsened during the course of the study.

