### **8.2. Analysis**

Descriptive analyses will be applied to summarize patients' demographic and baseline characteristics, and qualitative and quantitative assessments of the flortaucipir F 18 PET image.

Adverse events including injection site reactions will be summarized in terms of number and percentage of subjects experiencing an AE. The summary will be further broken down by system organ class (SOC) and preferred term using Medical Dictionary for Regulatory Activities (MedDRA) terms. Adverse events will also be presented by severity, relationship to treatment and seriousness. All subjects who experience SAEs or who discontinue due to AEs will be summarized.

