6.6.2 Adverse Events

The investigator's verbatim term of adverse events will be mapped to system organ class (SOC) and preferred terms using the current version of the Medical Dictionary for Regulatory Activities (MedDRA).

Treatment-emergent AEs (TEAEs) are undesirable experiences, signs, or symptoms that begin or worsen in intensity or frequency at the time of or after the administration of study drug at the imaging visit, and prior to the end of observation windows defined as following: the TEAE window will be from injection of flortaucipir F 18 until 48 hours post flortaucipir F 18 injection. These will be recorded on the AE page of the electronic case report form (eCRF).

Serious AEs (SAEs) are events that result in one of the following outcomes or constitute one of the following events:

- Death
- Initial or prolonged hospitalization (other than that required by protocol; “social hospitalization” or any hospitalization for non-medical reasons does not constitute an SAE
- A life-threatening experience (that is, immediate risk of dying)
- Persistent or significant disability/incapacity
- Congenital anomaly/birth defect
- Considered significant by the investigator for any other reason

Important medical events that may not result in death, are life-threatening, or require hospitalization may be considered serious adverse drug events when, based upon appropriate medical judgment, they may jeopardize the patient and may require medical or surgical intervention to prevent one of the outcomes listed in this definition.

For the summarization of TEAEs by seriousness, events recorded with missing seriousness will be summarized as serious.

Investigators will be instructed to report their assessment of the potential relatedness of each AE to protocol procedure or study drug. The assessment of the relationship of an AE to the administration of the investigational product is a clinical decision based on all available information at the time of the completion of the eCRF. For the summarization of TEAEs by relationship to study drug or protocol procedure, events recorded with missing relationship will be summarized as Related.

In addition to assessing the relationship of the administration of the investigational product to AEs, an assessment is required of the severity of the event. The following classifications should be used:

Mild:

A mild AE is an AE, usually transient in nature and generally not interfering with normal activities.

Moderate:

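### The SAP's only serious-event table stops at 48 hours after injection, while Protocol 8.2 promises a summary of every subject with an SAE and Protocol 7.7.4 makes some SAEs outside that window reportable

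*SAP*

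**What the plan says.** Protocol 8.2 plans counts and percentages of subjects with adverse events, by system organ class, preferred term, severity, relationship and seriousness. It then adds: "All subjects who experience SAEs or who discontinue due to AEs will be summarized". The section nowhere limits this to treatment-emergent events.

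Protocol 7.7.4 collects SAEs of any cause from dosing to 48 hours. Outside that window collection is conditional. SAEs after 48 hours are "not required to be reported unless the investigator feels the events were related to either investigational product or a protocol procedure". For SAEs after consent but before dosing, "the event will NOT be reported unless the investigator feels the event may have been caused by a protocol procedure".

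Protocol 7.7.2 also states: "The end of study, for the purpose of adverse event reporting, is defined as 48 hours after the last administration of flortaucipir F 18".

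SAP 6.6.2 sets the window used in the tables: "the TEAE window will be from injection of flortaucipir F 18 until 48 hours post flortaucipir F 18 injection". All seven summaries in SAP 8.11.2 are restricted to TEAEs. The only one on seriousness is item 6, "All Serious TEAEs by system organ class (SOC) and preferred term". All other adverse events go to listings. SAP 5.2 records no change from the protocol's planned analyses.

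**The concern.** The protocol creates a class of SAEs that are reportable although they fall outside the 48-hour window, and it commits to summarizing subjects with SAEs without excluding that class. The SAP tables have no place for them.

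The class is small but not arbitrary. After 48 hours an SAE must be reported only if an investigator thinks the tracer or a study procedure was responsible. The time limit therefore removes from the summary the late events that bear most directly on tracer safety. Expanding the safety database is the study's secondary objective, and summary tables are often quoted without the listings behind them. Item 6 could show no serious event although one judged related had been reported to the sponsor.

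**Working it through.** This is a comparison of texts. The plan gives no figure to reproduce.

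**Step 1. Which SAEs does each section cover?** For a subject who was dosed:

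| SAE onset | Reportable under Protocol 7.7.4 | Within the wording of Protocol 8.2 | Counted in SAP 8.11.2 item 6 |
|---|---|---|---|
| After consent, before injection, possibly caused by a protocol procedure | Yes | Yes | No, unless it worsens within 48 hours after injection |
| Injection to 48 hours, any cause | Yes | Yes | Yes |
| After 48 hours, judged related to product or procedure | Yes | Yes | No |
| After 48 hours, not judged related | Not required | Only if reported | No |

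The mismatch lies in the first and third rows. An event that begins within 48 hours and becomes serious later is still a TEAE and is counted.

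**Step 2. Can such events come to light?** Yes. Protocol 7.1.2 schedules a follow-up call no earlier than 48 hours after injection to ask about new adverse events. The flow chart in Protocol 11.2 marks SAE collection at screening and at that call.

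**Step 3. Does a listing satisfy the commitment to summarize?** The documents treat the two as different. Protocol 8.1 mentions listings separately from descriptive summaries, Protocol 8.2 describes the adverse event summary as numbers and percentages of subjects, and SAP 8.11.2 separates counts and percentages from listings.

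**Step 4. Size.** The documents plan about 500 enrolled subjects. The number dosed is not given, so 400 to 500 is assumed. The number of SAEs outside the window is also unknown. Suppose there is no serious TEAE.

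- One such subject: 1/500 = 0.20%, or 1/400 = 0.25%. Item 6 shows 0.
- Two such subjects: 2/500 = 0.40%, or 2/400 = 0.50%. Item 6 still shows 0.
- Exact (Clopper-Pearson) 95% limits, for scale only because the SAP plans none: 0/500 gives 0 to 0.74%; 1/500 gives 0.005% to 1.11%. These overlap heavily.

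**Step 5. How likely is at least one?** With 500 dosed and an assumed per-subject probability p of a late related SAE, the chance is 1 − (1 − p)^500:

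| Assumed p | Chance of at least one |
|---|---|
| 0.05% | 22% |
| 0.1% | 39% |
| 0.2% | 63% |
| 0.5% | 92% |

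The documents give no value for p, and with one scheduled contact after the window it may be lower than any of these. The table shows only that zero cannot be taken for granted.

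**The case against.** The best defence is that Protocol 8.2 should be read together with Protocol 7.7.2, which ends adverse event reporting at 48 hours and uses the same 48-hour definition of a TEAE. On that reading, an SAE experienced in the study after dosing is a serious TEAE, and item 6 delivers what was promised. This does not remove the conflict. Protocol 7.7.4 expressly keeps later related SAEs reportable, and new events are sought at a call made after 48 hours. Protocol 7.7.2 also distinguishes trial-emergent from treatment-emergent events, so a treatment-emergent limit could have been written into Protocol 8.2.

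Two parts of the defence stand. First, a fixed window is sound. SAEs inside it are collected regardless of cause and those outside it only on a causal judgement, so one pooled percentage would mix two collection rules. That is a reason to show the two groups separately. Second, it is not settled that a late SAE enters the clinical database. Protocol 7.7.3 and 10.7 point to an eCRF entry, but the 48-hour end of reporting in Protocol 7.7.2 leaves room for doubt.

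A reader might infer more than the documents support:

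- **That the tables would falsely report no related serious events.** No SAP table crosses relatedness with seriousness. Item 3, "All TEAEs by relationship to study drug, SOC, and preferred term", covers all TEAEs, and item 6 is not split by relatedness.
- **That discontinuations due to adverse events are lost in the same way.** Item 7, "All TEAE leading to study termination by system organ class (SOC) and preferred term", has the same window, but Protocol 5.1 ends participation when the scan is complete, so little remains to discontinue from. The disposition table in SAP 8.2 gives the reasons for discontinuation.
- **That leaving out never-dosed subjects is a mismatch.** Protocol 8.1.1 itself confines the safety population to dosed patients.
- **That the TEAE definition is wrong.** Both documents use the same 48 hours.

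**Conclusion.** The point holds for SAEs in dosed subjects. Protocol 8.2 commits to summarizing all subjects with SAEs, SAP 8.11.2 item 6 counts only those with onset or worsening from injection to 48 hours, and SAP 5.2 does not declare the difference. SAEs within the window are handled correctly.

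The expected numerical effect is small and may be nil. What could change is whether the summary says none or some. This rests on reading Protocol 8.2 as written and on the assumed number dosed. Whether the omitted events would at least be listed depends on their being entered in the eCRF, which is likely but not confirmed. The documents do not support extending the finding to the termination table, to never-dosed subjects or to the wording of the disposition section.

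**What to change.** In SAP 8.11.2:

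1. Keep item 6 unchanged.
2. Add one row, or a short separate table, with the number and percentage of safety-population subjects with any reported SAE regardless of onset. Show SAEs outside 0 to 48 hours separately, with the investigator's relatedness judgement.
3. Footnote that SAEs outside the window are collected only under the conditions of Protocol 7.7.4, so their frequency is not comparable with that inside it.
4. Confirm that these SAEs are entered in the eCRF or reconciled from the sponsor's safety database before the tables are run.

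If the sponsor intends to tabulate serious TEAEs only, SAP 5.2 should at least record this as a departure from Protocol 8.2.

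The cost is one row, one footnote and a check of data capture. No existing table is lost. If late SAEs are held only in the safety database, some reconciliation work is added. The reported SAE count may be slightly less favourable.

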8.11.3 Vital Signs

Vital signs (systolic and diastolic blood pressure, pulse, respiration rate) will be summarized using descriptive statistics.

All vital signs data will be presented in the listings.

8.11.4 Electrocardiogram (ECG)

Electrocardiogram (ECG) Results (Normal, Abnormal – Not Clinically Significant, Abnormal – Clinically Significant) will be summarized using counts and percentage.

All ECG data will be presented in the listings.

8.12 Pharmacodynamics

No pharmacodynamics analyses are planned for this study.

9 COMPUTER SOFTWARE

All analyses will be performed by Chiltern using SAS® Version 9.3 or later. All summary tables and data listings will be prepared utilizing SAS® software.

The standard operating procedures (SOPs) of Chiltern will be followed in the creation and quality control of all data displays and analyses.
